12.2 Exclusion Criteria

1	Pregnant or lactating (or gave birth within last year)
2	Age <18
3	Documentation of allergy or previous reaction to sugammadex
4	GFR <30
5	Neuromuscular disease (ICD codes)
6	Remain intubated/tach post-op

13.0 SUBJECT STATUS

Subjects will be classified as follows depending on their status:

- **Enrolled:** After meeting eligibility and being provided study drug from the OR pharmacy.
- **Withdrawn:** Meeting one of the conditions listed in the subject withdrawal section.
- **Subject completion:** Subjects will be considered to have completed this study upon successful confirmation of drug administration to the patient.

13.1 Subject Withdrawal

- Meeting any exclusion criteria that precludes subject's participation.
- In the Investigator's or IRB's opinion, a significant safety concern arises that requires subject discontinuation, or it is deemed that continued study participation is not in the subject's best interest.
- Study is terminated.

Investigators should follow withdrawn subjects with ongoing AEs until resolution according to standard of care.

13.2 Subject Discontinuation by Investigator

The Investigator, at their discretion, may discontinue a subject's enrollment into this study and/or withdrawal from the study. Should this occur, the reason for discontinuation will be documented onto the eCRF. All data collected prior to discontinuation may be used in the primary and secondary analysis.

14.0 SUBJECT RECRUITMENT

During the screening phase, patients aged 18 and older who will have a general anesthetic with either rocuronium or vecuronium and who are considered high risk for postoperative pulmonary complications will be flagged in CareConnect and enrolled in the study. Clinicians will receive an alert identifying the patient as a subject in the study and will remind the clinician to pick up the study drug sugammadex from the pharmacy.

15.0 HIPAA WAIVER OF AUTHORIZATION

Per the UCLA IRB, this study has received a HIPAA waiver of authorization for the entire study. PHI collected for the study from UC records will not be reused or disclosed, except in a de-identified format as indicated in the IRB.

16.0 INFORMED CONSENT PROCESS

This study has received a waiver of informed consent from the UCLA IRB, thus subject consent will not be required.

17.0 STUDY DATA COLLECTION

All aspects of the patient's management are at the discretion of the attending physician.

The following data will be collected and recorded in the eCRF:

Overall

- Admission ID
- Procedure name
- Primary CPT code
- Date of service
- UCLA location
- Case start time
- Case end time
- Procedure start time
- Procedure end time
- Emergency case status
- Case department name
- Obstructive respiratory lung disease
- OSA
- Preop SpO2
- BMI > 40
- Acute respiratory infection
- Airway pathology
- BMI > 35
- Multiple intubation attempts
- Surgery duration > 2 hrs
- Abdominal thoracic HN surgery
- Hgb less than 10 in 6 months
- Intraoperative sugammadex total?
- Sugammadex administered time
- Flag pushed in from PDW
- BPA fired in Epic
- Received rocuronium intraop
- Received study drug
- Enrolled patient
- PACU signout time
- Duration O2 saturation less than 90%
- Duration O2 saturation less than 95%
- Pathway compliance
- Postop reintubation
- Unplanned upgrade of care
- EARS study drug
- Inpatient death
- Bradycardia
- Anaphylaxis
- Reintubation

Baseline data

- Age

- Weight
- BMI
- ASA Physical Status Score
- Number of STOP Bang Criteria
- Existence of OSA on Problem List
- Previous Charting for OSA
- Previous Prescription for CPAP/BiPAP
- Lung Disease in problem list
- Abnormal PFT results
- Previous coding of lung disease
- Surgical procedure
- Oxygen saturation in preoperative area
- Preoperative Hemoglobin

Intraoperative Data

- Surgical duration
- Median PEEP
- Median TV
- Median FiO₂
- Maximum PEEP
- Maximum TV
- Maximum FiO₂
- Minimum PEEP
- Minimum TV
- Minimum FiO₂
- Time and dosage of administration of rocuronium
- Time, dosage and name of reversal agent
- All documented assessments of muscle strength (i.e. TOF ratio)
- Anesthesia Provider
- Time since most recent dosage of neuromuscular blocking agent
- Most recent train-of-four ratio prior to reversal.

PACU Data

- Time until ready to discharge
- Duration of supplemental oxygen therapy
- Minimum oxygen saturation
- Duration of oxygen saturation <95
- Duration of oxygen saturation <90
- Adverse events and protocol deviations, if applicable

18.0 SAFETY AND ADVERSE EVENTS

18.1 Definitions

The definitions for adverse event, serious adverse event, and unanticipated adverse effect are provided below.

18.2 Adverse Event (AE)

Adverse event shall mean any untoward medical occurrence in a Study subject who is administered the Study Drug regardless of whether or not a causal relationship with the Study Drug exists. By way of example and without limitation, an AE can be any unfavorable and unintended sign (for example, an abnormal laboratory finding), symptom, or disease temporally associated with the use of the Study Drug.

18.3 Serious Adverse Event (SAE)

Serious adverse event shall mean any untoward medical occurrence in a Study subject who is administered the Study Drug that results in death, a life-threatening drug experience, requires inpatient hospitalization or prolongation of existing hospitalization, results in persistent or significant disability/incapacity, or is a congenital anomaly/birth defect, cancer, or is a new cancer if the cancer is the condition of the study, or overdose. Other important medical events that may jeopardize the patient or may require intervention to prevent one of the outcomes listed previously should also be considered “serious”.

18.4 Suspected Unexpected Serious Adverse Reaction (SUSAR)

Suspected Unexpected Serious Adverse Reaction or “SUSAR” shall mean any Serious Adverse Event, the nature, severity or frequency of which is not consistent with information in the most current investigator’s brochure, or with respect to a marketed product the most current Summary of Product Characteristics (SPC) or Package Insert.

18.5 Sugammadex Common Adverse Reactions

Sugammadex is an FDA-approved drug. The Merck prescribing information for Bridion (sugammadex) includes vomiting, pain, nausea, hypotension, and headache as the most common adverse reactions reported. In a small number of patients, the following known outcomes have occurred: anaphylaxis and marked bradycardia.

The list of SAEs and SUSARs for study reporting includes:

- Unplanned upgrade of care
- Unexpected transition in patient status
- Reintubation
- Bradycardia
- Anaphylaxis
- Death

19.0 RECORDING OF ADVERSE EVENTS

- All Adverse Events occurring within 48 hours of drug administration, regardless of seriousness, severity or relationship to the study drug, must be recorded in the eCRF and will include a detailed event description, date of onset, date investigator first aware, whether the event is serious, investigator's assessment of severity, relationship to study drug, action taken with respect to the study drug, corrective treatment/therapy given, additional assessments performed, outcome, and date of resolution/stabilization of the event.
- Any pre-existing medical condition that is present at the time of screening will not be reported as an AE, unless the condition worsens during the course of participation. The occurrence of diagnostic or elective surgical procedures for a pre-existing condition will not be recorded as an AE, unless the condition becomes more severe or results in an AE.
- Whenever possible, diagnosis or single syndrome should be reported instead of symptoms.
- The investigator should take appropriate measures to follow all AEs until resolution or until progression has been stabilized, or until study exit, to ensure the safety of the subjects. If the AE continues beyond the period of subject enrollment in the study and/or the date the subject withdraws from the study, clinical investigators should follow the subjects according to standard of care.
- All SAEs will be followed until the Investigator deems the event to be chronic or the adherence to be stable or until the subject exits the study. Other supporting documentation of the event may be requested by the Sponsor and should be provided as soon as possible.
- All subject deaths, regardless of relationship to the study drug, should be reported.
- Each AE will be coded using the Medical Dictionary for Regulatory Activities (MedDRA) and presented based on the system organ class and preferred term.

20.0 Guidelines for Reporting AE

20.1 Serious Adverse Event and Suspected Unexpected Serious Adverse Reaction Reporting to Sponsor

Principal Investigator shall forward to Merck's Global Pharmacovigilance ("Merck GPV") group, any SAE or SUSAR, including, but not limited to, all initial and follow-up information involving any Study subject in the Study. Notification shall be in the form of a completed CIOMS I/MedWatch (or other mutually agreed upon format) **within two (2) business days of but not longer than three (3) calendar days of receipt of the information**. This information shall be transmitted to Merck GPV using the contact information provided below or such other modified contact information as provided by Merck in writing. All information shall be transmitted in the English language and contain the reporter's name and the Study subject identifier code. SUSAR information will be reported unblinded if the Study Drug has been blinded in the Study. Randomization codes for all other SAEs will be provided to Merck GPV at end of Study if the Study Drug has been blinded in the Study.

All reports of Study Drug exposure during pregnancy or lactation, whether associated with an AE or not, must be reported to Merck GPV in accordance with the timelines and contact information for an SAE. Principal Investigator shall follow pregnancies to term to obtain the outcome of the pregnancy. The outcome of the pregnancy shall be forwarded to Merck GPV.

Institution and Principal Investigator shall fully comply with all of their respective reporting obligations to the applicable regulatory authorities with respect to any AE, SAE or SUSAR that arises from the Study.

SAE reports and any other relevant safety information are to be forwarded to Merck GPV [contact].

20.2 POST-APPROVAL (PA) REPORTING TO THE IRB

The PI must report to the IRB adverse events that meet all three of the following criteria

- Unexpected;
- Related or possibly related to research participation; and
- Places participants or others at greater risks of harm than was previously known or recognized (not described in or of greater severity or frequency than described in the IRB-approved protocol and/or consent form)

In reviewing (internal or external) adverse events, the IRB ***may request additional follow-up information***. These can include autopsy results or terminal medical reports for an unexpected study-related death.

For all adverse events (internal or external) that meet the above criteria, the IRB ***may require additional action*** in response to the event in order to ensure that the research continues to meet the criteria for approval under 45 CFR 46.111 and/or 21 CFR 56.111. This may include:

- revision of the consent form to include risk(s) identified as a result of this event
- re-consent of enrolled participants continuing study treatment
- notification to previously enrolled participants and/or participants in long-term follow-up
- protocol changes to address and minimize newly identified risk(s)
- suspension of enrollment or all study procedures
- termination of the research

Those AEs that the IRB agrees meet the above criteria will receive the determination of *Unanticipated Problems involving risks to subjects or others* under 45 CFR 46.108(a)(4)(i), 21 CFR 56.108(b)(1), 21 CFR 312.53(c)(1)(vii) and/or 21 CFR 312.66.

- The IRB will report that determination to the appropriate federal department(s) and UCLA institutional officials as required.

Initial and follow-up reports of AEs that meet the reporting criteria should be submitted to provide the IRB with complete information on the adverse event. Adverse event findings associated with the study drug will be followed until the event resolves or stabilizes at a level acceptable to the Principal Investigator.

20.3 DEADLINES FOR SUBMISSION TO THE IRB

- **Within 3 business days of learning of the event:** *Internal or External Adverse events meeting the above criteria resulting in **death, suspension, suspension or termination of the research***
- **Within 10 business days of learning of the event:** All other *reportable adverse events meeting the above criteria*
- No PAR submission (maintain in study files):
 - Internal or external adverse events that **do not meet** the above criteria
 - External AEs where the investigator **does not yet know** whether or not the event placed the participants or others at increased risk
 - Follow-up reports of external AEs that do not provide information on increased severity of the event since the initial report to the IRB
- No PAR submission (summarize at continuing review):
 - Deaths that are related and expected

All Adverse Events must be reported to the Sponsor and IRB in accordance with the following timeline:

Type of Reportable Event	Reporting Schedule to Sponsor	Reporting Schedule to IRB
AE		Follow local IRB reporting requirements as discussed in section 20.3
SAE	Within 2 calendar days or 3 days total after the Investigator is first aware.	SAE / Patient death shall be reported in accordance with local requirements.
SUSAR	Within 2 calendar days or 3 days total after the Investigator is first aware.	SAE / Patient death shall be reported in accordance with local requirements.

The study Sponsor will report safety events to the FDA as required per 21 CFR 812. Sponsor reporting requirements are as follows:

- The PI is responsible for classification of adverse events, reviewing investigators' assessment of adverse events, and reporting to IRBs and regulatory agencies, and to Data Safety Monitoring Committee. If results of the

evaluation of an unanticipated adverse effect were determined to be an unreasonable risk, the PI shall notify the IRB, and participating investigators within 10 working days after the Sponsor first receives notice of the unanticipated adverse effect. The IRB is responsible for informing regulatory agencies if an AE meets the criteria listed in 20.2 and it receives the determination of Unanticipated Problems involving risks to subjects or others.

22.0 PROTOCOL DEVIATIONS (“PD”)

All efforts should be made to avoid any protocol deviation. Any deviation from the requirements outlined in this protocol will be considered a protocol deviation. A protocol deviation that may affect the scientific soundness of the protocol or the rights, safety, or welfare of the patients should be reported to the IRB and applicable regulatory authorities. Other deviations are those that occur in direct association with a specific study patient. These include, but are not limited to, deviations from inclusion/exclusion criteria, protocol-specified procedures and assessments, and study drug handling and usage. All protocol deviations and their reasons will be reported to the study sponsor, documented in the eCRF and protocol deviation log.

23.0 GUIDELINES FOR REPORTING PDS TO THE IRB

Investigators are required to keep a log of all deviations/Incidents.

Only the subset of those deviations that the PI determined have affected the rights and/or welfare of participants or others must be submitted to the IRB for review. However, the entire log may be reviewed by OHRPP Quality Improvement Unit (QIU) and the log should be submitted at continuing review for those studies that are subject to continuing review.

The following information/assessments should be recorded in the Investigator’s deviation/incident log:

- Date of event
- Subject ID
- Date the investigator was made aware of the event
- A description of the event
- Is this an initial event or a follow-up/update on a previous event?
- Does the deviation meet the threshold for reporting to the IRB?
- Who (which member of the study team) made the assessment of whether or not the deviation met the threshold for IRB reporting via PAR?
- Date the assessment made (of whether it met the threshold for IRB reporting via PAR)
- Date of submission to the IRB (if applicable)
- PAR# (if applicable)

A subset of deviations/incidents must be submitted via PAR application for timely review:

Deviations/incidents for which the answer to any of the following questions is “yes” should be submitted to the IRB for review via PAR application:

- 1) Did the deviation/incident cause the participant or someone else to be at risk of potential harm?
- 2) Was the participant or someone else actually harmed by the deviation/incident?
- 3) Does the deviation/incident negatively affect the rights of participants or others?
- 4) Does an individual deviation not meet the above criteria, but there are 4 or more of the same type of minor deviation in a study and those deviations, taken as a group, suggest a pattern of non-compliance on the part of the study team or ancillary staff?
- 5) Does an individual deviation not meet the above criteria, but there are 4 or more of the same type of minor deviation in a study and those deviations, taken as a group, suggest a pattern of non-compliance on the part of the study team or ancillary staff?

Root cause Analyses

For all PAR applications describing deviations that meet the criteria for reporting (either single occurrence or aggregate) the investigator should conduct a quality improvement review that includes a root cause analysis. This is necessary to determine if there are underlying systems problems that led to this deviation.

Corrective Action Preventive Action (CAPA) plan

Once a root cause has been identified, a CAPA plan must be developed by the investigator and included in materials submitted to the IRB. The CAPA should address two areas:

- 1) How will the deviation be resolved for the participant(s) who has already experienced the event? (does the participant require additional monitoring, should the participant be informed, does the participant need to be approached for re-consent or be asked to provide HIPAA authorization, etc.)
- 2) How will research procedures be modified to prevent similar deviations in the future? (does the study need an eligibility checklist, should the order process with pharmacy for study drug be updated, do study team members with greater clinical experience need to administer instruments, etc...)

For deviations related to HIPAA authorizations or breach of confidentiality for UCLA Health- related research records, study team will consult with UCLA Health Office of Compliance Services to develop the CAPA plan. The CAPA developed with UCLA Health Office of Compliance Services must be provided to the IRB for a final determination

24.0 WITHDRAWAL OF IRB/EC APPROVAL

An investigator shall report to the sponsor a withdrawal of approval by the investigator's reviewing IRB as soon as a possible.

25.0 POWER ANALYSIS AND SAMPLE SIZE DETERMINATION

25.1 Retrospective analysis

In order to assess the change in time to readiness for PACU discharge and postoperative respiratory dysfunction (duration of oxygen saturation below 90%) after the introduction of sugammadex we will construct two models. First, we will utilize propensity score matching (PSM)¹⁴ to adequately risk balance the patients pre/post sugammadex introduction (variables mentioned in section 2.4). We will use the nearest-neighbor PSM approach and start with a caliper of width equal to 0.2 of the standard deviation of the logit of the propensity score (as described by Austin¹⁵). We will assess balance of the covariates pre/post intervention by computing

standardized mean differences (SMD) for each variable and will use the rule of thumb “SMD less than 0.1”¹⁶ to indicate adequate balance. Finally, we will also construct a table of patient characteristics pre/post matching to see how well the algorithm balanced the patients. If individual covariates are not adequately balanced with the default propensity score matching algorithm, we will try different matching parameters until adequate balance is achieved (e.g. change the caliper size for what we consider a match and/or run a more advanced propensity score model including interaction or squared terms).

After adequate balance is observed, we will compare our outcomes of interest between pre/post periods using a linear (or log-linear) model for time to readiness and logistic regression for our binary outcome (postoperative respiratory dysfunction) using the propensity matched dataset. An interrupted time-series (also known as segmented regression) analysis as described by Wagner¹⁷ will be conducted for each outcome to estimate the pre-intervention time trend, immediate impact of intervention (change-point), as well as reliably estimating the slope change after the intervention. All estimates of interest from these models will be summarized with p-values and 95% confidence intervals.

Statistical analyses will be performed using R V3.5.1 (Vienna, AU) using the “*Match*” package for propensity score matching and p-values <0.025 (for our two primary outcomes) will be considered statistically significant utilizing the Bonferroni adjustment (0.05/2).

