At this point, we estimate that the pathway will recommend sugammadex for all patients in the medium or high-risk groups as well as some patients in the low risk group (i.e. those patients requiring deep neuromuscular blockade to facilitate surgical conditions such as robotic procedures, free flap cases and others). Given the large number of patients, Merck would supply one vial of study drug for each patient. Thus the total amount of study drug would be no more than 6,500 patients for the one year intervention time.

Given 1 year of data, we observed an overall average PACU discharge time of 152.54 minutes (SD=623.86). With one year of post-data, we are adequately powered (90%) to pick up a reduction in PACU discharge time as small as 27.04 (two-sample t-test, alpha=0.025). Since the current difference in PACU discharge time between low and high risk groups is 67.52 (subtracting 216.62-149.10, see table), we feel the 27.04 minimally detectable difference gives us a great chance of detecting a meaningful difference.

Given 1 year of data (pre-period), we observed the rate of patients with any time SpO2<90% was 4.6% (574/12,467). With one year of post-data, we are adequately powered (90%) to pick up a reduction in this rate if it decreases to around 3.7% in the post (chi-square test, alpha=0.025). Since the current difference in patients with any time with SpO2<90% between low and high risk patients is 5.2% (subtracting 9.2%-4.0%), we feel the minimally detectable difference of 3.7% (4.6%-3.8%) is feasible.

Table 2.

	suppl O2, mean (SD)	PACU disch. Time, mean (SD)	Reintubation, freq (%)	Unplanned upgrade, freq (%)	SpO2<90%, freq (%)	SpO2<95%, freq (%)
OVERALL(n=13,277)	74.81 (241.82)	152.54 (623.86)	89 (0.7%)	138 (1.0%)	574 (4.6%)	6510 (52.3%)
low (n=9,841)	74.48 (280.55)	149.10 (599.78)	63 (0.6%)	111 (1.1%)	372 (4.0%)	4603 (50.0%)
medium(n=2,997)	74.98 (95.67)	154.43 (536.58)	23 (0.8%)	22 (0.7%)	164 (5.8%)	1658 (58.8%)
high (n=439)	79.54 (88.44)	216.62 (1321.46)	3 (0.7%)	5 (1.1%)	38 (9.2%)	249 (60.9%)
Smallest detectable difference (90% power)	9.61	24.84	0.4%	0.4%	3.8%	50.3%

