- Preexisting respiratory disease: The presence of obstructive or restrictive lung disease as defined based on the structured data in the EMR such as previous PFT results, previous medication and previous diagnoses. For analysis purposes patients will be divided into low, medium and high risk groups based on the extent of their disease.

Statistical Methods:

All analysis will be performed by the study team at UCLA.

Retrospective analysis: In order to assess the change in time to readiness for PACU discharge and postoperative respiratory dysfunction (duration of oxygen saturation below 90%) after the introduction of sugammadex we will construct two models. First, we will utilize propensity score matching (PSM) to adequately risk balance the patients pre/post sugammadex introduction. We will use the nearest-neighbor PSM approach and start with a caliper of width equal to 0.2 of the standard deviation of the logit of the propensity score. We will assess balance of the covariates pre/post intervention by computing standardized mean differences (SMD) for each variable and will use the rule of thumb “SMD less than 0.1” to indicate adequate balance. Finally, we will also construct a table of patient characteristics pre/post matching to see how well the algorithm balanced the patients. After adequate balance is observed, we will compare our outcomes of interest between pre/post periods using a linear (or log-linear) model for time to readiness and logistic regression for our binary outcome (postoperative respiratory dysfunction) using the propensity matched dataset. An interrupted time-series (also known as segmented regression) analysis as described by Wagner will be conducted for each outcome to estimate the pre-intervention time trend, immediate impact of intervention (change-point), as well as reliably estimating the slope change after the intervention. All estimates of interest from these models will be summarized with p-values and 95% confidence intervals.

Statistical analyses will be performed using R V3.5.1 (Vienna, AU) using the “Match” package for propensity score matching and p-values <0.05 will be considered statistically significant.

Prospective analysis: The prospective analysis will largely follow a similar framework however we will focus on the primary and secondary outcomes as described above and will use a one year period prior to implementation as our baseline.

Power/Sample Size:

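### The matched-set outcome models state no adjustment covariates, so imbalance left under the SMD 0.1 tolerance passes into the period effect; adjusting for covariates already collected is a cheap improvement

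*Combined protocol and SAP*

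**What the plan says.** Section 25.1 of the protocol uses nearest-neighbour propensity matching of the pre and post periods. Balance is judged by "standardized mean differences (SMD) for each variable and will use the rule of thumb" "SMD less than 0.1". If a covariate fails, "we will try different matching parameters until adequate balance is achieved"; the SAP's Statistical Methods section leaves that step out. The matched periods are then compared "using a linear (or log-linear) model for time to readiness and logistic regression for our binary outcome". The SAP words it the same way: "After adequate balance is observed, we will compare our outcomes of interest between pre/post periods using a linear (or log-linear) model". Neither text states any adjustment covariate for these models.

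Both also plan, for each outcome, "An interrupted time-series (also known as segmented regression) analysis as described by Wagner", again with no case-mix covariates stated. The propensity variables are given only as "variables mentioned in section 2.4", and the supplied document has no such section (Section 2.0 is the abbreviations table). Section 25.2 says the prospective analysis will largely follow the same approach, with the year before implementation as baseline. Section 26.0 sizes the study "to pick up a reduction in PACU discharge time as small as 27.04 (two-sample t-test, alpha=0.025").

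**The concern.** This is a before/after comparison without a concurrent control, so case-mix control rests mainly on the matching. Matching to a tolerance leaves some imbalance behind. If the outcome model contains only the period term, the prognostic part of that imbalance is counted as an effect of sugammadex or of the pathway, or hides a real one, depending on its direction.

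Sample size makes this worth attention. With about 13,000 patients per period the standard error is small, so a bias that would vanish in the noise of a smaller study can become a noticeable fraction of it. More patients shrink the standard error but not the bias.

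**Working it through.** **Inputs.** From Section 26.0 and Table 2: PACU discharge time mean 152.54 min, SD 623.86; detectable difference 27.04 min at alpha 0.025 and 90% power; SpO2<90% in 4.6% (574/12,467), detectable down to about 3.7%; risk classes low, medium and high with n = 9,841, 2,997 and 439, mean times 149.10, 154.43 and 216.62 min, and SpO2<90% rates 4.0%, 5.8% and 9.2%. Study-drug ceiling: 6,500 patients. Balance limit: SMD 0.1.

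**1. Reproduce the plan's figure.** For a two-sided test, n per period = 2 × [(2.241 + 1.282) × 623.86 / 27.04]² = 13,213. This agrees with the 13,277 of Table 2 and the 13,127 of Table 1. The standard error of the difference is 623.86 × √(2/13,213) = 7.68 min, and 27.04/623.86 = 0.043 outcome SD.

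**2. Convert an imbalance into a bias.** The SMD is in units of the covariate's own SD. A covariate with correlation r to the outcome moves the outcome by r outcome SDs for each covariate SD, so

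bias = SMD × r × outcome SD.

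At SMD 0.1 this is 0.1 × 623.86 × r = 62.4 × r min. Type I error is the probability that a normal variate shifted by bias/SE falls beyond ±2.241.

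**3. The strength of prognosis that Table 2 shows.** Score each risk class at its own outcome mean. The shares are 0.741, 0.226 and 0.033.

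- PACU time: the class means deviate from 152.54 by −3.44, +1.89 and +64.08 min. The weighted squares sum to 8.75 + 0.81 + 135.79 = 145.35, so the between-class SD is 12.06 min and r = 12.06/623.86 = 0.019. The bias at SMD 0.1 is 1.2 min, or 0.16 SE, and type I error is 2.7%.
- SpO2<90%: the deviations from 4.58% are −0.58, +1.22 and +4.62 points. The between-class SD is 1.14 points against an outcome SD of 20.9 points, so r = 0.054. The bias is 0.11 points. With SE = √(2 × 0.046 × 0.954/12,467) = 0.265 points, this is 0.43 SE and type I error is 3.9%. The detectable drop is 0.9 points.

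**4. Assumed stronger prognosis.** Here r is the combined value when the imbalances all sit at 0.1 and lean the same way; three independent covariates with r = 0.1 each act like r = 0.3. The SE is 7.68 min with 13,213 per period and 623.86 × √(2/6,500) = 10.94 min with 6,500.

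| Assumed r | Bias, PACU time | Type I error, 13,213 per period | Type I error, 6,500 per period |
|---|---|---|---|
| 0.1 | 6.2 min | 7.8% | 5.0% |
| 0.2 | 12.5 min | 26.9% | 13.6% |
| 0.3 | 18.7 min | 57.8% | 29.8% |

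For SpO2<90% the same r values give 0.1 × r × 20.9 = 0.2, 0.4 and 0.6 points.

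**5. What it would take to mimic the detectable effect.** r = 27.04/62.4 = 0.43, which is about 19% of the outcome variance. Reaching the significance boundary, 2.241 × 7.68 = 17.2 min, needs r = 0.28.

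**The case against.** A reader might set 0.1 beside 0.043 and infer that the plan accepts an imbalance more than twice the effect it seeks. The documents do not support that. The first figure is in covariate SDs and the second in outcome SDs, so the ratio of 2.3 describes a bias only for a covariate perfectly correlated with PACU time.

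The rest of the case against is serious. The 0.1 is the most that is tolerated, and caliper matching may do much better: at SMD 0.02 and r = 0.3 the bias would be 0.02 × 0.3 × 623.86 = 3.7 min. The only prognostic strength the documents give for the two primary outcomes is Table 2, where the inflation is slight. The prospective phase is limited to 6,500 study-drug patients, which roughly halves the larger error rates. The before/after-matching table would show what imbalance remains, and the time series deals with gradual drift. Stating no covariates is also silence, not a commitment to an unadjusted model.

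All of that stands, and it lowers the severity. It does not remove the point. Section 26.0 itself calls the risk classes much simplified and says they omit severity of illness. The very large SD, four times the mean, suggests extreme values that may hold r down in minutes; r could be larger under the permitted log-linear model. Section 4.0 reports postoperative desaturation of 21% at BMI 18.5 to 25 and more than 40% at BMI 30 to 45. Taken as two groups at 21% and 40%, with an assumed 20% to 60% in the heavier one, that is r of about 0.18 to 0.21. The saturation threshold is not given there, so this cannot be carried over to SpO2<90%. Finally, the time series states no case-mix covariates, so an abrupt change in case mix would load onto its level-change estimate.

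**Conclusion.** The gap holds in a limited form. The matched-set models as written state nothing that would remove imbalance left within the tolerance, in a study sized for 0.043 outcome SD. On the documents' own risk classes the damage at the ceiling is slight: 1.2 min and 0.11 points, with type I error of 2.7% and 3.9% against 2.5%. The range of 8% to 58% (5% to 30% with 6,500 per period) rests on three assumptions: a combined r of 0.1 to 0.3, imbalances at the ceiling, and all of them in one direction. It also uses the protocol's alpha of 0.025 and a matched set with no further losses. Nothing in the documents shows that these conditions will occur, and nothing excludes them. A reader might infer that the primary tests will reject far too often; that has not been shown. This is a cheap improvement worth making, not a defect that must be cured before the study can proceed.

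**What to change.** In Section 25.1 and the SAP's Statistical Methods section:

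- State that the matched-set linear or log-linear and logistic models contain the period term together with the pre-intervention propensity covariates, and list them in place of the reference to a section that cannot be found. Candidates are age, BMI, ASA status, OSA, lung disease, preoperative SpO2, haemoglobin, procedure group and hospital. Leave out anything the pathway itself can change.
- Keep the SMD limit of 0.1 as a diagnostic only.
- Fix the matched set before outcome variables are joined, since the protocol allows repeated re-matching.
- Say in Section 25.2 that the same applies to the prospective comparison.

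The cost is SAP wording and a few lines of code. Section 17.0 already collects these variables or the fields to derive them (procedure name and CPT code for procedure group, location for hospital). No new patients or data are needed.
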